6.2.2. Prohibited Concurrent Medications/Therapies

While receiving treatment with KZR-261, enrolled subjects may not receive investigational or approved anticancer agents including cytotoxic chemotherapy, targeted therapies, or therapeutic monoclonal antibodies.

Palliative radiation is permitted only for symptom management and with a narrow radiation port (eg, solitary bone lesion). Sponsor review and approval is required before administration of palliative radiation while on study treatment.

7. STUDY PROCEDURES

7.1. Schedule of Study Procedures

Schedules of study procedures for the Screening Period, Treatment Period, and the Follow-up Period (including visit windows) are presented in the Schedule of Events ([Appendix A](#) and [Appendix B](#)).

Details regarding the specific blood draw requirements for each visit are outlined in the Laboratory Manual provided to each study site.

7.2. Description of Study Procedures

Prior to undergoing any study-specific procedures/assessments (except those consistent with standard of care for management of the underlying malignancy), all potential subjects must sign an informed consent form (ICF) describing the study with sufficient information for subjects to make an informed decision regarding their participation per [Section 11.3](#).

The following sections provide details of the procedures to be performed.

7.2.1. Medical History

Documentation of the subject's medical history should contain the subject's full medical history including prior and concomitant illnesses/diseases, concomitant medications, and demographic data. Historical cancer data and diagnostic information, including tumor mutational profile if known, will be captured in the eCRF. Prior imaging reports may be requested.

7.2.2. Physical Examination

A complete physical examination including collection of body weight will be conducted at Screening and Baseline and should include assessments of at least the following systems: head and neck, dermatological, respiratory, cardiovascular, abdomen, extremities, neurological, and musculoskeletal. Height will be collected at the Screening visit only.

A symptom-directed abbreviated physical examination including collection of body weight will be conducted at all other study visits indicated in the Schedule of Events ([Appendix A](#) and [Appendix B](#)).

Subjects will be asked at each visit that includes a physical examination about mouth dryness, salivary gland pain and sensitivity, and urinary and ejaculation issues. Treatment-emergent, medically significant changes from baseline in physical examination will be recorded as AEs.

7.2.3. Pregnancy Testing and Reproduction Precautions

Women of childbearing potential must have a negative serum β -hCG pregnancy test result at Screening. Negative serum or urine pregnancy tests will be required at all other visits indicated in the Schedule of Events ([Appendix A](#) and [Appendix B](#)). The Screening visit test should be performed within 2 weeks prior to initiation of study treatment or in closer proximity to the treatment start-date as required by local/institutional regulations. A positive urine pregnancy test result should be confirmed by a serum pregnancy test.

The subject must agree to use highly effective contraceptive methods or abstinence for the duration of time on the study and continue to use acceptable contraceptive methods for 3 months after administration of the last dose of study treatment. Highly effective contraception is defined as the use of 2-barrier methods (eg, female diaphragm and male condom) or 1 barrier method with spermicide, intrauterine device, or hormonal contraceptives (eg, implant or oral). If the subject is using a hormonal form of contraception, use must have been stable for at least 4 weeks prior to Screening, and if using concomitant mycophenolate, the subject must use another nonhormonal form of highly effective contraception. Abstinence will be acceptable only if it is in line with the preferred and usual lifestyle of the subject. Periodic abstinence (eg, calendar, ovulation) and withdrawal are not acceptable methods of contraception.

Male subjects with female partners of childbearing potential must be congenitally sterile or surgically sterile (vasectomy with confirmation of aspermia) or agree to use 2 effective methods of contraception including one barrier method (eg, condom with spermicide and contraception by female partner) for the duration of time on the study and for 3 months after administration of the last dose of study treatment. Use of a condom is required by men during intercourse with a male or female partner to prevent potential delivery of the drug via seminal fluid during the study until the EOT visit.

7.2.4. *Electrocardiogram*

ECGs will be performed at the timepoints indicated in the Schedule of Events ([Appendix A](#) and [Appendix B](#)). Note that some study visits have pre-treatment and multiple post-treatment ECG timepoints. Additional ECGs are required during Cycle 4 ([Appendix B](#)).

Vital sign measurements should be performed per institutional guidelines, preferably prior to ECGs. A 12-lead ECG is performed 10 minutes after the subject has been in the supine position. The Investigator or qualified designate will review and indicate if the ECG is normal or abnormal, and if abnormal, whether clinically significant. Any medically significant changes from the Screening ECG will be recorded as an AE.

7.2.5. *Vital Sign Measurements and Oxygen Saturation*

Vital signs measurements (including systolic and diastolic blood pressure, pulse rate, respiration rate, and body temperature) and oxygen saturation will be collected at all study visits. Blood pressure and pulse should be collected after the subject has had at least 5 minutes of rest in the seated position. If blood pressure is elevated on the first measurement at Screening or Baseline, it should be repeated after an additional 5 minutes of rest. It is recommended that blood pressure is measured using the same arm at each assessment. When the time of vital signs measurement coincides with a blood sample collection, vital signs will be measured per institutional guidelines.

7.2.6. *Ocular Examination*

Slit lamp and visual acuity examinations will be conducted to monitor for cataracts and should be reviewed prior to administration of KZR-261 at the beginning of each cycle where an eye examination is required ([Appendix A](#) and [Appendix B](#)). Any medically significant changes from the Screening evaluation will be recorded as an AE.

7.2.7. Tumor Specimens for Biomarkers

Tumor biopsies will be requested pre-treatment. Although a fresh sample is preferred, submission of an adequate tumor specimen (paraffin block) collected within 1 year before the subject's first dose of KZR-261 will be acceptable for subjects where a fresh sample cannot be obtained. If a paraffin block is not available, a minimum of 10 and up to 20 5- μ m unstained slides should be provided. For any subject who provided a tumor sample pre-treatment, a biopsy of accessible tumor tissue will be requested at either the end of Cycle 2 (Days 21-28 of Cycle 2) or at PD, whichever comes first.

Pre-treatment tumor biopsies (fresh only) will be required for subjects enrolled in the All-Tumors expansion cohort in Part 2A (exceptions to this requirement may be considered after discussion with the Medical Monitor); an additional biopsy of accessible tumor tissue will be required at either the end of Cycle 2 (Days 21-28 of Cycle 2) or at PD, whichever comes first.

7.2.8. Clinical Laboratory Evaluations

Collection of blood and urine samples for clinical laboratory evaluations are outlined in the Schedule of Events for Cycles 1 and 2 ([Appendix A](#)) and Cycle 3+ ([Appendix B](#)).

Clinical laboratory tests for safety (hematology, serum chemistries, urinalyses, coagulation tests, serum pregnancy) and other tests during scheduled visits will be performed at the clinical trial site or an alternative, licensed local testing facility. Pregnancy tests, urine or serum, may be performed at the study site using a licensed test. Abnormal safety laboratory results that are considered clinically significant should be repeated as soon as possible (preferably within 24–48 hours).

Subjects who are HBsAg negative and hepatitis B core antibody positive with no detectable DNA at Screening will require regular monitoring of hepatitis B virus DNA at the discretion of the Investigator.

Unscheduled or additional laboratory tests with results reported by local laboratories may be performed if immediate results are necessary for management of treatment-emergent AEs or dosing determination. Unless otherwise noted, when scheduled simultaneously with a dosing visit, results of laboratory evaluations should be reviewed prior to administration of study drug.

Detailed instructions for sample collection, processing, storage, and shipment will be provided in the Laboratory Manual. It is recommended that the smallest appropriate sampling tubes be used for local laboratory sample collection to curtail blood loss due to phlebotomy.

7.2.8.1. Hematology

Blood samples for hematology testing will be collected at timepoints detailed in the Schedule of Events ([Appendix A](#) and [Appendix B](#)). Hematology parameters shown in [Table 8](#) will be analyzed according to standard methods at a local laboratory.

Table 8: Hematology Tests

Hematology Tests

• Hemoglobin• Hematocrit• White blood cell (WBC) count (total and differential)• Red blood cell (RBC) count• Platelet (PLT) count• Mean corpuscular volume (MCV)• Mean corpuscular hemoglobin (MCH)• Mean corpuscular hemoglobin concentration (MCHC)

7.2.8.2. Serum Chemistry

Blood samples for serum chemistry testing will be collected at timepoints detailed in the Schedule of Events ([Appendix A](#) and [Appendix B](#)) while the subject is in a fasting state (no food or caloric drinks after an overnight fast or other fasting period lasting at least 6 hours). Clinical chemistry parameters shown in [Table 9](#) will be analyzed according to standard methods at a local laboratory.

Table 9: Clinical Chemistry Tests

Serum Chemistry Tests (Fasting)

• Creatinine• Blood urea nitrogen (BUN)• Aspartate aminotransferase (AST)• Alanine aminotransferase (ALT)• Alkaline phosphatase (AP)• Total bilirubin• Serum albumin• Serum total protein• Sodium• Bicarbonate (HCO_3)• Potassium• Chloride• Glucose• Phosphate (PO_4)• Calcium• Amylase• Lipase• Triglycerides

7.2.8.3. Urinalysis

Urinalysis testing will be performed according to standard methods at a local laboratory. Dipstick testing is acceptable.

7.2.8.4. Coagulation Parameters

Blood samples for analysis of coagulation parameters will be collected at timepoints detailed in the Schedule of Events ([Appendix A](#) and [Appendix B](#)). Coagulation parameters to be analyzed are presented in [Table 10](#). For coagulation parameter tests, either PT or INR may be measured, and either PTT or aPTT, depending on institutional standards. Blood samples for coagulation parameter tests must be collected within 24 hours prior to all biopsy procedures.

Table 10: Coagulation Tests

Coagulation Tests

• International normalized ratio (INR) or prothrombin time (PT)• Partial thromboplastin time (PTT) or activated partial thromboplastin time (aPTT)

7.2.8.5. Hemoglobin A1c (HgbA1c)

Blood samples for quantitation of HgbA1c will be collected at timepoints shown in the Schedule of Events ([Appendix A](#) and [Appendix B](#)).

7.2.9. Tumor Markers

If tumor markers in blood (eg, PSA, CA-125, carcinoembryonic antigen [CEA], CA-15.3, CA-19.9) are known to be elevated, they should be measured at timepoints shown in the Schedule of Events ([Appendix A](#) and [Appendix B](#)).

7.2.10. Response Assessments

Assessments of response and progression will occur in accordance with RECIST v1.1 ([Eisenhauer et al., 2009](#)) at timepoints shown in the Schedule of Events ([Appendix A](#) and [Appendix B](#)). Subjects with mCRPC will be assessed per PCWG3 guidelines ([Scher et al., 2016](#)).

All subjects must have contrast-enhanced imaging studies of chest, abdomen, and pelvis as well as other areas of suspected disease within 28 days prior to their first dose of study treatment. The preferred imaging modality is contrast-enhanced computed tomography (CT). In subjects for whom IV contrast for CT is contraindicated, perform contrast-enhanced magnetic resonance imaging (MRI) scanning of the aforementioned anatomic regions with non-contrast enhanced CT of the chest. Subjects known to have fluorodeoxyglucose (FDG)-avid tumors are required to undergo positron emission tomography (PET) scanning along with the CT scan at Screening. Subjects whose tumors demonstrate FDG update at Screening should undergo follow-up PET scanning post-Cycle 6, post-Cycle 12, and every 6 cycles thereafter (see below). Subjects with skin, subcutaneous or lymph node metastases may also have evaluations of measurable lesions (including measurements, with a ruler or calipers) by means of physical examination.

Subjects with mCRPC must have a baseline PSA and bone scan in addition to the aforementioned imaging studies. (Note: A rising PSA as the sole indicator of disease activity will not lead to a determination of disease progression.) On-treatment bone scans will be performed at the same time points as CT/MRI scans. As a rule, the same imaging modality (ie, CT or MRI or combined CT/PET scans) should be used for all scheduled tumor assessments and measurements.

Imaging studies should be repeated prior to Cycle 3 (ie, end of Cycle 2) and every 2 cycles thereafter (ie, end of Cycles 4, 6, 8, etc). There is a 7-day window for imaging procedures to allow time for availability of results prior to the next cycle. If an imaging procedure must be scheduled to occur outside the 7-day window, this should be discussed with the Medical Monitor for approval prior to the procedure.

Response assessments, including imaging studies, are to be performed at the EOT visit, if PD has not already been established and the last response assessment was conducted >4 weeks prior to EOT.

Subjects who discontinue study treatment for reasons other than PD will be contacted by telephone approximately every 90 days for 12 months after last study treatment for evidence of PD, collection of information about subsequent anti-tumor therapy, and assessment of survival status. Subjects who discontinue study treatment for PD will be contacted by telephone approximately every 90 days for 12 months after last study treatment for assessment of survival status.

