Subjects will receive KZR-261 for up to 6 cycles. Upon completion of Cycle 6, a subject who is deriving clinical benefit may continue treatment at the discretion of the Investigator and with agreement of the Medical Monitor. Study treatment will be discontinued at any time for unacceptable AEs, progressive disease, voluntary withdrawal by the subject, another discontinuation criterion is met, or study closure by the Sponsor (Section 8.1.2).

Following discontinuation of study treatment, subjects will complete an End of Treatment (EOT) visit as soon as possible after their last dose of study treatment (Section 8.3). Safety follow-up will be conducted by telephone 30 days after the subject's last dose of study treatment (Section 9.1.5). If AEs have not resolved at that time, additional safety follow ups will occur approximately every 30 days until resolution of AEs or until, in the opinion of the Investigator, the event is stabilized or determined to be chronic.

Subjects who discontinue study treatment for reasons other than progressive disease (PD) will be contacted by telephone approximately every 90 days for 12 months after last study treatment for evidence of PD, collection of information about subsequent anti-tumor therapy, and assessment of survival status. Subjects who discontinue study treatment for PD will be contacted by telephone approximately every 90 days for 12 months after last study treatment for assessment of survival status.

Safety will be assessed as described in [Section 2.2.1.1](#).

Anti-tumor activity will be assessed as described in [Section 2.2.2.1](#), with assessments of response conducted after every 2 treatment cycles.

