6. DOSAGE AND TREATMENT ADMINISTRATION

6.1. Treatment Administration

For all subjects, KZR-261 will be administered as a 30- to 60-minute IV infusion via a central line on Days 1, 8, and 15 of a 4-week (28-day) treatment cycle. An IV infusion pump or syringe pump will be used for all infusions.

Further details regarding drug product formulation, preparation, and administration of KZR-261 will be provided in a separate Pharmacy Manual.

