6.1.3. Criteria for Initiation of a New Cycle

To commence treatment in Cycle 2 and beyond, subjects must meet the following criteria:

- ANC $\geq 1.25 \times 10^9/L$
- Hemoglobin $\geq 8 \text{ g/dL}$
- PLT count $\geq 75 \times 10^9/L$
- Serum creatinine $\leq 1.5 \times \text{ULN}$ (local institution) or calculated creatinine clearance $>60 \text{ mL/min}$ by the Cockcroft-Gault formula
- Total bilirubin $\leq 1.5 \times \text{ULN}$ (local institution)
- AST and ALT $\leq 3 \times \text{ULN}$ (local institution) or ALT and AST $\leq 5 \times \text{ULN}$ if the subject has hepatic metastases
- FBS $<200 \text{ mg/dL}$
- Serum amylase and lipase values $\leq 1.5 \times \text{ULN}$ (local institution)
- Average QTcF $<470 \text{ msec}$
- Resolution to \leq Grade 2 or baseline of any previously reported Grade 3 or 4 event

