6.1.5. Missed Doses

Study treatment should be administered within the visit windows as per the Schedule of Events ([Appendix A](#) and [Appendix B](#)), with an exception for delays in dosing for up to 7 days duration for resolution of toxicity. Missed doses as a result of patient non-compliance will be considered protocol deviations.

Subjects who do not fulfill treatment interruption criteria ([Section 6.1.2](#)) or meet Individual Subject Stopping Rules ([Section 8.1.2](#)) may miss up to 2 consecutive doses or up to 6 doses in total over the first 6 cycles for any reason (eg, AE, scheduling, emergency). Subjects who require more than two dose reductions, or who miss one entire cycle because of an AE(s) must permanently discontinue KZR-261. Missed doses due to implementation of Study Stopping Rules ([Section 8.1.1](#)) should be discussed with the Medical Monitor to evaluate whether KZR-261 should be discontinued.

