- ^j Imaging should be repeated prior to Cycle 3, prior to Cycle 5 (ie, end of Cycle 4) and every 2 cycles thereafter (ie, end of Cycles 4, 6, 8 etc.). There is a 7-day window around imaging procedures to allow time for result availability prior to the next cycle. If an imaging procedure must be scheduled to occur outside the 7-day window allowance, this should be discussed with the Medical Monitor for approval prior to the procedure. Imaging should be repeated at EOT if the last response assessment was >4 weeks prior. Tumors will be measured according to RECIST v1.1. Subjects with mCRPC will be assessed per PCWG3 guidelines. All subjects with mCRPC will have bone scans at the same time points as the imaging procedures. Subjects with skin, subcutaneous, or lymph node metastases may also have tumor evaluations (including measurements, with a ruler or calipers) by means of physical examination.
- ^k Day 28 assessments of the prior cycle may be combined with Day 1 of the next cycle. Whenever possible, these evaluations should be referred to as the End of Cycle evaluation (for the earlier cycle) as opposed to the beginning of cycle evaluation for the subsequent cycle.
- ^l Subsequent to discontinuation of study treatment, subjects will have an EOT visit as soon as possible following their last KZR-261 dose and prior to initiation of follow-on anticancer therapy. Safety follow-up by telephone will occur approximately 30 days after the subject's last dose of study treatment. If AEs have not resolved at that time, additional safety follow-ups will occur approximately every 30 days until AE resolution or until, in the opinion of the Investigator, the event is stabilized or determined to be chronic.
If a subject attending a Day 28 or Day 1 visit meets criteria for EOT, the EOT visit assessments should be conducted instead of Day 28/Day 1 assessments.

- ^m Subjects who discontinue study treatment for reasons other than PD will be contacted by telephone approximately every 90 days for 12 months after last study treatment for evidence of PD, collection of information about subsequent anti-tumor therapy, and assessment of survival status. Subjects who discontinue study treatment for PD will be contacted by telephone approximately every 90 days for 12 months after last study treatment for assessment of survival status.

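### On-treatment scans follow completed cycles while PFS runs in calendar weeks, so late cycle starts make assessment timing depend on toxicity and can shift the PFS landmarks and CBR

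*Protocol*

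**What the plan says.** **Imaging schedule.** Protocol 7.2.10: "Imaging studies should be repeated prior to Cycle 3 (ie, end of Cycle 2) and every 2 cycles thereafter". Protocol 3.1 describes the design "with assessments of response conducted after every 2 treatment cycles", and the imaging footnote of Appendix B reads "Imaging should be repeated prior to Cycle 3, prior to Cycle 5 (ie, end of Cycle 4) and every 2 cycles thereafter". The SAP appendices repeat the schedule. The imaging window also refers to the cycle: "There is a 7-day window for imaging procedures to allow time for availability of results prior to the next cycle". Neither document says that imaging stays on calendar time when a cycle starts late.

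**Cycle timing.** Dosing is "on Days 1, 8, and 15 of a 4-week (28-day) treatment cycle" (Protocol 6.1). Protocol 6.1.3 makes each new cycle conditional on recovery: "To commence treatment in Cycle 2 and beyond, subjects must meet the following criteria", followed by blood count, liver, glucose, pancreatic enzyme, QTcF and adverse event conditions. Protocol 6.1.5 holds dosing to the visit windows "with an exception for delays in dosing for up to 7 days duration for resolution of toxicity". It also says that subjects who "miss one entire cycle because of an AE(s) must permanently discontinue KZR-261".

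**Endpoints.** SAP 13.2.3 measures PFS from first dose to documented progression or death, with landmarks at 17 weeks (PFS4) and 26 weeks (PFS6). CBR counts stable disease only if it holds over at least two consecutive assessments (Protocol 10.5.5), and it decides futility at 15 subjects in each Part 2A tumor-specific cohort (Protocol 10.6). Part 2B randomizes 1:1 between two doses (Protocol 3.4), and data are summarized by dose within tumor type (SAP 7.4). No analysis addresses assessment timing.

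**The concern.** Progression on imaging is dated by the scan that shows it. If a cycle starts late because toxicity has not resolved, the next scan is also late, and progression that has already occurred is recorded later. The PFS clock does not pause.

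Two doses with the same true PFS but different rates of late cycle starts would then show different PFS4 and PFS6. Part 2B sets two doses side by side to support the RP2D. If the higher dose causes more late starts, as is plausible, the landmark rates could flatter it.

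The same mechanism affects CBR in the opposite direction. Stable disease must last to a later second scan, so a toxic schedule makes the Part 2A futility hurdle slightly harder to clear.

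**Working it through.** The plan states no power, event count or delay rate for PFS, so there is no figure of its own to reproduce. The delay shares and true medians below are assumptions.

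**1. Scan dates.** The end of Cycle 2k falls on day 56k if nothing slips. Scan k comes after 2k−1 cycle starts that can slip (Cycles 2 to 2k). With d days lost at each, scan k falls on day 56k + d(2k−1).

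| Slip at each start | Scan 1 | Scan 2 | Scan 3 |
|---|---|---|---|
| 0 days | 56 | 112 | 168 |
| 3 days | 59 | 121 | 183 |
| 7 days | 63 | 133 | 203 |

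The last row is weeks 9, 19 and 29.

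**2. Landmarks.** Week 17 is day 119, 7 days after nominal scan 2. Week 26 is day 182, 14 days after nominal scan 3. With scans at cycle end, a cumulative delay of more than 7 days by the end of Cycle 4 moves scan 2 past the PFS4 landmark. More than 14 days by the end of Cycle 6 does the same to scan 3 and PFS6.

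**3. PFS4 with no true difference.** Assume exponential PFS with median 91 days, so S(t) = 2^(−t/91); progression seen only at scans; no dropout; scans at cycle end; and each cycle start slipping 7 days with probability p. Then S(56) = 0.6528, S(63) = 0.6189, S(112) = 0.4261 and S(119) = 0.4040.

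Three starts (Cycles 2, 3, 4) precede scan 2. With no slip it falls on day 112, and with one slip on day 119. With two or three it falls after the landmark, and only scan 1 counts. So

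PFS4 = (1−p)³·S(112) + 3p(1−p)²·S(119) + p²(1−p)·S(56) + [2p²(1−p) + p³]·S(63)

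- p = 0.1: 0.729×0.4261 + 0.243×0.4040 + 0.009×0.6528 + 0.019×0.6189 = 42.6%
- p = 0.3: 0.343×0.4261 + 0.441×0.4040 + 0.063×0.6528 + 0.153×0.6189 = 46.0%
- p = 0.5: 0.125×0.4261 + 0.375×0.4040 + 0.125×0.6528 + 0.375×0.6189 = 51.8%
- p = 0: 42.6%; p = 1: 61.9%

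| Starts delayed | PFS4, more v less delayed | Difference (points) | Same, true medians 70 and 120 days |
|---|---|---|---|
| 30% v 10% | 46.0% v 42.6% | +3.4 | +3.6, +2.9 |
| 50% v 10% | 51.8% v 42.6% | +9.2 | +9.8, +8.1 |
| 100% v 0% | 61.9% v 42.6% | +19.3 | +20.6, +17.1 |

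Simulation with 100,000 subjects per arm gives 52.2% v 42.6% for the middle row, hence 9 to 10 points.

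**4. PFS6 and median.** By the same method PFS6 moves by about +1, +5 and +8 points at a true median of 91 days. The observed median jumps between scan dates, so its direction is not fixed. At a true median of 91 days it is 119, 126 and 133 days in the more-delayed arm v 112. At 120 days with 100% v 0% it is 133 v 168, because S(112) = 2^(−112/120) = 0.524 is above one half and S(133) = 2^(−133/120) = 0.464 is below it.

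**5. CBR.** The stable-disease part needs no progression through scan 2. This is S(112) = 42.6% with no delay and S(133) = 2^(−133/91) = 36.3% with 7 days lost at every start.

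**6. Imaging window.** If every scan is done exactly 7 days early, scan 2 falls on day 105 plus the slips, so up to 14 days are absorbed (105 + 14 = 119). Then

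PFS4 = (1−p)³·S(105) + 3p(1−p)²·S(112) + 3p²(1−p)·S(119) + p³·S(56), with S(105) = 0.4494.

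This gives 44.3%, 43.6% and 44.9% at p = 0.1, 0.3 and 0.5, so the two milder biases almost vanish. The extreme case remains (65.3% v 44.9%). A scan 6 days early does not absorb a second 7-day slip (106 + 14 = 120), and 30% v 10% again gives a gap of 3.6 points (48.2% v 44.6%).

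**7. After the change.** With scans on days 56, 112 and 168 at both doses, PFS4 is 42.6% at both.

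**The case against.** Much can be said for leaving the schedule alone.

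- **Delays are bounded.** A reader might infer that a cycle can slip until a whole cycle is missed. Protocol 6.1.5 allows toxicity delays of up to 7 days, so that reading is not supported; the working uses 7 days. Withheld doses are not made up (Protocol 6.1.4), so a dose skipped within a cycle need not move the scan. Late cycle starts are what matter.
- **The window helps.** Step 6 shows that scanning on the first permitted day removes nearly all of the PFS4 bias in the milder cases. The protocol does not require that day, so this is a mitigation and not a safeguard.
- **Other events dilute the effect.** Deaths count when they occur. The end-of-treatment scan, required if the last was more than 4 weeks earlier, can act the other way for subjects who stop for toxicity. It does nothing for those who are delayed and continue.
- **The comparison is imprecise and descriptive.** No between-dose PFS test is planned, and the RP2D rests on the totality of results. With 15 per dose and a rate near 0.43, the 90% margin on a difference is 1.645×√(2×0.43×0.57/15) = 0.30, or ±30 points. A bias of 3 to 10 points is small beside that. This stands, but imprecision does not cancel a systematic shift that could recur in each tumor type.
- **No delay figures are given.** More late starts at the higher dose is a fair expectation, since the MTD targets a DLT rate near 30% and a Cycle 2 delay of more than 7 days for an AE is itself a DLT. The size of any difference is unknown.

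**Conclusion.** The concern holds in limited form. The mechanism is clear from the text: scans follow cycles, cycles wait for recovery, and PFS and its landmarks run on calendar time. Confidence in that is high.

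Confidence in the size is medium. Under the stated assumptions and cycle-end scanning, PFS4 favors the more-delayed dose by about 3 points at 30% v 10%, 9 to 10 at 50% v 10%, and 19 at 100% v 0%, which is an extreme. PFS6 moves less. Early scanning within the window can reduce the milder figures to almost nothing.

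Three stronger readings are not supported. The first is that PFS is always prolonged at the more toxic dose: the median can move either way, and CBR falls with delay. The second is that a formal error rate is inflated: no between-dose test exists, so the harm is to an informal dose judgment. The third is that comparisons between Part 2A cohorts are distorted: none is planned, and no claim is made about them.

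The change is worth making because it is cheap and scans not taken on time cannot be recovered in analysis. It ranks between a suggestion and a recommendation.

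**What to change.** In Protocol 7.2.10, 3.1 and the imaging footnotes of Appendices A and B, and in the matching SAP appendices, schedule imaging and mCRPC bone scans every 8 weeks ±7 days from Cycle 1 Day 1 while on treatment, regardless of dose holds or cycle delays. Define the assessment timepoints for CBR and PFS by these weeks (Protocol 10.5.5; SAP 13.2.3 and 13.2.5). Optionally, add to SAP 13.2.3 a PFS sensitivity analysis that uses scheduled assessment dates or interval censoring.

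The cost is amendment wording and a matching SAP edit. Subjects with no delay keep their present scan dates. In delayed subjects a scan may not fall on a cycle-boundary visit and may come somewhat earlier than now.
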